#### **4.4 Sample size calculation**

The performed power analysis (power= 80%, alfa=5% two-sided) calculated a required sample size of  $2 \times 36 = 72$  patients. The analysis was based on an expected 50% decrease of the percentage of patients for whom placement of hemostatic staples was required peroperatively.

## 5. TREATMENT OF SUBJECTS

### 5.1 Investigational product/treatment

In the intervention group, patients will be administered tranexamic acid 1500 mg intravenous at induction of the procedure. In the control group, patients will receive a placebo infusion with sodium chloride.

### 5.2 Use of co-intervention (if applicable)

Not applicable.

### 5.3 Escape medication (if applicable)

Not applicable.

## 6. INVESTIGATIONAL PRODUCT

### 6.1 Name and description of investigational product(s)

Tranexamic acid injections, 100 mg/ml, ampoule 5 ml. It is a competitive inhibitor of plasminogen and therefore of the conversion into plasmin in the fibrinolytic system. In high doses, tranexamic acid is a non-competitive plasmin inhibitor(11).

### 6.2 Summary of findings from non-clinical studies

The clinical studies as mentioned in paragraph 6.3 provide the most up-to-date and applicable information.

For details see the IMPD of tranexamic acid.

### 6.3 Summary of findings from clinical studies

Tranexamic acid (TA) is a plasminogen inhibitor that can be used to inhibit fibrinolysis during or after surgery and thus minimize the risk of developing perioperative hemorrhage. Little is known about the use of TA in bariatric surgery. Nevertheless, in several other surgical areas such as for coronary-artery surgery and arthroplasty, perioperative administration of TA has proven its value in preventing postoperative hemorrhage (6-8). Up until now, the use of TA to prevent postoperative hemorrhage in bariatric surgery is once described by Hussain et al.(9). The authors performed a meta-analysis of administration of TA during laparoscopic sleeve gastrectomies and concluded that administration of TA is a simple yet effective way to lower the rates of staple line hemorrhage, while shortening the length of surgery. In the end of 2018, Klaassen et al described that reoperations may be prevented due to postoperative administration of TA in case of a suspicion of an already present hemorrhage(10).

### 6.4 Summary of known and potential risks and benefits

Side effects of tranexamic acid include dose-dependent gastrointestinal complaints in 1-10% (nausea, vomiting, diarrhea); allergic skin reactions in 0.1-1%; and

thrombocytopenia, thromboembolic events, blindness, color blindness and other visual disorders in 0.01-0.1%.

Benefits of tranexamic acid include the prevention of perioperative hemorrhage in several surgical areas (6-9) and treatment of postoperative hemorrhage and herewith prevention of reoperation after bariatric surgery(10).

### **6.5 Description and justification of route of administration and dosage**

For general (non-topical) fibrinolysis in adults, tranexamic acid is administered intravenously in a dosage of 15 mg/kg bodyweight in a solution with sodium chloride. Administration can be repeated every 6-8 hours. In our study population, body weight varies between 100 and 200 kg. Tranexamic acid has a small volume of distribution (0.12-0.17 mg/kg). The acid part of tranexamic acid is in a physiological pH deprotonated and the amino part is protonated. Therefore, we expect that the molecule will mostly be present in watery environment and will not spread to the fatty tissue. Therefore, we expect that a dosage above 1500 mg will not be of additional value.

### **6.6 Dosages, dosage modifications and method of administration**

A set dose of 1500 mg will be used, based on the study population with morbid obesity. It will be administered intravenous dissolved in 100 ml sodium chloride 0.9% in a time frame of 15-30 minutes, with a maximum of 100 mg/min.

### **6.7 Preparation and labelling of Investigational Medicinal Product**

The Investigational Medicinal Product will be ordered according to local procedures at the Department of Pharmacy in the [REDACTED] and will be brought to the OR by the principal investigator. Preparation and labelling of the investigational medicinal products is done according to the relevant GMP guidelines for Good Manufacturing Practice by the hospital's pharmacy.

### **6.8 Drug accountability**

The local Department of Pharmacy can provide all the medication that is required for this trial.

## **7. NON-INVESTIGATIONAL PRODUCT**

### **7.1 Name and description of non-investigational product(s)**

Placebo, saline injection fluid produced by Baxter.

### **7.2 Summary of findings from non-clinical studies**

The placebo contains a saline solution which has no effect on fibrinolysis.

### **7.3 Summary of findings from clinical studies**

### **7.4 Summary of known and potential risks and benefits**

### **7.5 Description and justification of route of administration and dosage**

### **7.6 Dosages, dosage modifications and method of administration**

100 ml sodium chloride 0.9% will be administered in a time frame of 15-30 minutes.

### **7.7 Preparation and labelling of Non Investigational Medicinal Product**

The non-investigational product will be ordered according to local procedures at the Department of Pharmacy in the [REDACTED] and will be brought to the OR by the principal investigator. Preparation and labelling of the non-investigational products is done according to the relevant GMP guidelines for Good Manufacturing Practice by the hospital's pharmacy.

### **7.8 Drug accountability**

The local Department of Pharmacy can provide all the medication that is required for this trial.

## **8. METHODS**

### **8.1 Study parameters/endpoints**

#### **8.1.1 Main study parameter/endpoint**

Primary outcome measure is peroperative use of hemostatic staples.

#### **8.1.2 Secondary study parameters/endpoints (if applicable)**

Secondary outcome measures are the decrease in hemoglobin after the procedure at 1 day postoperative, rates of postoperative hemorrhage (i.e. hemorrhage needing administration of packed cells or a surgical or radiological re-intervention) within 30 days postoperative and rates of VTE within 3 months postoperative.

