## SUMMARY

**Rationale:** Fast-track protocols are frequently used in bariatric surgery and often include short-term thromboprophylaxis and short length of hospital stay. These treatment strategies may negatively affect the occurrence and diagnosis of postoperative hemorrhage. Over the years, the rates of venous thromboembolic events (VTE) decrease, while there seems to be an increase in the occurrence of postoperative hemorrhage. Tranexamic acid (TA) is a plasminogen inhibitor which inhibits fibrinolysis. Peroperative administration of TA may lower the incidence of postoperative hemorrhage.

**Objective:** This trial aims to investigate if peroperative administration of TA can reduce the peroperative and postoperative hemorrhage rates in laparoscopic sleeve gastrectomy.

**Study design:** This is a double-blind, single center randomized controlled trial.

**Study population:** Patients eligible for bariatric surgery according to the IFSO guidelines and undergoing a laparoscopic sleeve gastrectomy. Patients unwilling to give informed consent, patients with a medical history of bleeding or VTE and patients that use therapeutic anticoagulants will be excluded.

**Intervention (if applicable):** Patients are randomized between 2 groups: 1) Single dose of 1500 mg TA to be administered during induction of the procedure by anesthesiologist, and 2) Standard protocol with administration of placebo infusion.

**Main study parameters/endpoints:** Primary outcome measure is peroperative use of hemostatic clips. Secondary outcome measures are the decrease in hemoglobin after the procedure, rates of postoperative hemorrhage (i.e. hemorrhage needing administration of packed cells or a surgical or radiological re-intervention) and rates of VTE.

**Nature and extent of the burden and risks associated with participation, benefit and group relatedness:** All patients will be required to undergo one additional blood drawing in the week prior to the procedure which will be performed at their weighing appointment, meaning that this will not require an extra hospital visit. TA has very little side effects. Therefore we conclude that the expected benefits of the intervention outweigh the minor risks involved.

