## 2. OBJECTIVES

Primary Objective: Does the peroperative administration of TA lead to lesser use of peroperative extra hemostatic clips?

Secondary Objective(s): Does the peroperative administration of TA lead to a smaller hemoglobin decrease 1 day postoperatively and a lower reoperation rate within 30 days postoperative due to hemorrhage, or an increase in venous thromboembolic events within 3 months postoperative?

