### 10.1 Primary study parameter(s)

Differences in use of hemostatic staples (yes/no) between the 2 groups will be determined using Chi-Square tests. The difference in hemoglobin decrease will be tested using multivariate linear regression analysis, correcting for comorbidities (hypertension, diabetes, dyslipidemia) and use of hemostatic staples. These same analyses will be performed to assess the differences in amount of patients needing to undergo a re-

intervention, but adding administration of postoperative tranexamic acid as a covariate. Results will be evaluated at a significance threshold of  $p < 0.05$  (two-sided).

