### **10.2 Secondary study parameter(s)**

Differences in rates of DVT (yes/no), PE (yes/no) and in rates of administration of postoperative tranexamic acid (yes/no) between the 2 groups will be calculated using Chi-Square (Fisher's Exact) tests.

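### The declared postoperative haemorrhage endpoint has no stated test: Section 10.1 analyses re-intervention instead, and files this and haemoglobin under the primary heading

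*Protocol*

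**What the plan says.** The protocol describes the bleeding outcome in four places.

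- **Summary:** the secondary outcomes include "rates of postoperative hemorrhage (i.e. hemorrhage needing administration of packed cells or a surgical or radiological re-intervention) and rates of VTE". No time window is given.
- **Section 2 (secondary objective):** the question is whether tranexamic acid (TA) leads to "a lower reoperation rate within 30 days postoperative due to hemorrhage".
- **Section 8.1.2 (secondary endpoint):** "rates of postoperative hemorrhage (i.e. hemorrhage needing administration of packed cells or a surgical or radiological re-intervention) within 30 days postoperative".
- **Section 10.1 (analysis):** "These same analyses will be performed to assess the differences in amount of patients needing to undergo a" re-intervention, with postoperative TA added as a covariate.

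Section 10.2 lists DVT, PE and postoperative TA, and contains no haemorrhage or transfusion outcome. Section 8.3 says that packed cells and postoperative haemorrhage are taken from the electronic patient file.

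On hierarchy, Section 8.1.1 names one primary outcome, peroperative use of hemostatic staples (clips in the Summary and Section 2). Section 10.1, headed as the primary analysis, holds the chi-square test for that outcome, the haemoglobin regression and the re-intervention analysis. One significance threshold closes the section.

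**The concern.** Objective, endpoint and analysis should describe the same variable. Here the endpoint is a composite of transfusion and two kinds of re-intervention, the objective is one part of it, and the analysis uses a variable that is narrower in one respect and wider in two others. An analyst who follows Section 10 to the letter never tests what Section 8.1.2 declares, and an author could report any of the three as the planned bleeding result.

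Bleeding is the clinical reason for the trial, and so few events are expected that the choice of definition can decide what is reported. The placement of two secondary analyses under the primary heading adds a smaller ambiguity about which test carries the trial's claim.

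**Working it through.** **1. The plan's own figure.** The only calculated figure is 2 × 36 = 72 (Section 4.4), for clip or staple use. Inputs: control rate 63.3% (Section 1); a 50% decrease, giving 31.65%; two-sided 5%; power 80% (Section 4.4). With unpooled variance:

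n per arm = (1.960 + 0.842)² × (0.633 × 0.367 + 0.3165 × 0.6835) / 0.3165² = 35.15, rounded up to 36, or 72 in total.

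The figure reproduces, and haemorrhage plays no part in it.

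**2. The wordings side by side.** Each row is a possible patient; each column says whether that patient is an event as the text stands.

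| Patient | 8.1.2 | Section 2 | 10.1 |
|---|---|---|---|
| Bleed, reoperated by day 30 | yes | yes | yes |
| Bleed, radiological re-intervention by day 30 | yes | no | yes |
| Bleed, packed cells only, by day 30 | yes | no | no |
| Re-intervention for another cause | no | no | yes, as worded |
| Bleed, re-intervention after day 30 | no | no | yes, as worded |

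The second row takes reoperation in Section 2 to mean surgery. The last row can arise because follow-up runs to 3 months (Section 12.5). All three wordings agree only on the first row.

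**3. How much one patient matters.** Inputs: 2.2% haemorrhage after sleeve gastrectomy in this centre (Section 1); 100 patients, equally allocated (Section 3).

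- Expected events with the same rate in both arms: 100 × 0.022 = 2.2.
- Chance of no event at all: 0.978^100 = 0.108.
- If TA halved the rate (an assumption made here; the 50% in Section 4.4 concerns staples): 50 × 0.022 + 50 × 0.011 = 1.65 events.
- One patient in an arm of 50 is 1/50 = 2 percentage points, about as large as the whole 2.2% rate. A 2–0 split is 4% against 0%; with one patient reclassified it is 2% against 0%.

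**4. Could significance turn on it?** With k events all in one arm of 50, the two-sided Fisher p-value is 2 × C(50,k)/C(100,k). This gives 0.056 for k = 5 and 0.027 for k = 6. At about two expected events, no definition is likely to reach 0.05. What changes is the reported count and difference.

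**5. The test itself.** Section 10.1 refers back to the preceding analyses, which are a chi-square test and a linear regression, so the method for this yes/no outcome is unclear. If the regression is meant, it carries three comorbidities, staple use and postoperative TA besides treatment arm, for about two events. Such a model cannot be usefully estimated.

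**The case against.** **There is one formal definition.** The Summary and 8.1.2 agree apart from the window; Section 2 is an objective and Section 10.1 names an analysis variable. Re-intervention is part of the composite and is analysed. This stands, and it limits the point: what lacks a test is the composite, and with it the transfusion-only bleeds. A reader might infer that haemorrhage is not analysed at all; the text does not support that.

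**A statistical analysis plan may settle it.** It may, but this is not a detail left open. The protocol already fixes an analysis, of a different variable from its endpoint, so a later plan would have to depart from 8.1.2 or from 10.1.

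**Re-intervention in 10.1 is probably meant as re-intervention for bleeding within 30 days.** That is plausible, since 8.3 lists haemorrhage rather than re-intervention of any cause. It removes the last two rows of the table but leaves the transfusion-only row.

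**Three co-primary outcomes.** A reader might infer from the 10.1 heading that three outcomes are tested as primary, with a false-positive risk of up to 1 − 0.95³ = 14.3%. The Summary, Section 2, Section 4.4 and Section 8.1.1 all fix clip or staple use as the single primary outcome, and a test on about two events would not spend its full 5%. The figure does not describe this trial.

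**Postoperative TA.** Section 6.4 credits TA with "treatment of postoperative hemorrhage and herewith prevention of reoperation after bariatric surgery", so a reader might infer that bleeds treated with TA are ignored. They are not: 10.1 enters postoperative TA as a covariate and 10.2 compares its rate between arms. Whether such adjustment is sound is a separate question. Counting TA use in the endpoint would be a preference, and needs a reason for giving it that 8.3 does not list.

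**VTE.** Testing DVT and PE separately is no material fault. At the centre's 0.05% rate, 100 patients give 0.05 expected events.

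**Conclusion.** The point holds in this form. Followed as written, the plan analyses a different variable from the haemorrhage endpoint it declares, and the objective names a third. Two secondary analyses also stand under the primary heading; that is a misplacement, because the rest of the protocol leaves no doubt about the primary outcome.

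The size is modest. The endpoint is secondary, the sample size does not rest on it, and about 2.2 events are expected. One reclassified patient can change the reported difference by 2 percentage points, though it is unlikely to change a significance statement. This rests on the centre's 2.2% applying to trial patients and on 100 being enrolled; at 72 patients the expected count is 72 × 0.022 = 1.58. Section 1 does not say which definition the 2.2% uses, and the documents do not say how many bleeds are managed by transfusion alone, so the number of events lost cannot be estimated. The wording should be corrected before unblinding.

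**What to change.** - **Section 2:** replace the reoperation wording with the 8.1.2 composite and its 30-day window; add the window to the Summary.
- **Section 10:** make that composite, restricted to haemorrhage and to 30 days, the analysed variable. Compare it once between arms with Fisher's exact test, which 10.2 already names, in place of the reference back to the earlier analyses. The components can be listed by arm as description.
- **Sections 10.1 and 10.2:** keep only the test of clip or staple use in 10.1, and move the haemoglobin and haemorrhage analyses to 10.2 as secondary.

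The cost is a change of wording in the Summary and in Sections 2, 10.1 and 10.2. Section 8.3 already collects packed cells and postoperative haemorrhage; event dates are needed to apply the window. Sample size, visits and treatment do not change.

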#### **8.1.3 Other study parameters (if applicable)**

Comorbidities such as hypertension, diabetes en dyslipidemia will be taken into account. Also, the peroperative blood pressure and the duration of surgery will be registered.

### **8.2 Randomisation, blinding and treatment allocation**

After obtaining informed consent at the outpatient clinic of the surgical or anesthesiological department, patients will be randomized into 1 of the 2 groups using Variable Block Randomization software by Ciwit B.V. (Castor EDC). Patients will either receive tranexamic acid or placebo (sodium chloride) during induction. Patient, surgical team and anesthesiological team will be blinded for the treatment, as the hospital pharmacy will prepare the infusion bags for each individual patient.

Availability of the patient's individualized infusion bag will be checked at the Time Out Procedure (TOP). The coordinating researcher is unblinded in order to be able to consult the treatment arm in case of emergency.

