### **3. STUDY DESIGN**

This is a double-blind, single center randomized placebo-controlled trial that will last for approximately 1 year, depending on the speed of inclusion. We aim to include 100 patients.

Patients are equally randomized between 2 groups: 1) Single dose of TA to be administered during induction of the procedure by anesthesiologist, and 2) Standard protocol with administration of a placebo (sodium chloride).

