### **8.3 Study procedures**

An extra blood sample (1 EDTA tube) is obtained in the week preoperative by venipuncture. From this blood sample, hemoglobin tests are performed in the hospital's laboratory. Postoperative hemoglobin value will be obtained from the blood sample that is performed in all bariatric patients on the first postoperative day. Information on peroperative use of hemostatic staples, administration of packed cells, postoperative tranexamic acid, rates of postoperative hemorrhage and VTE are obtained from the electronic patient file. Routine venous duplex ultrasound will not be performed. Therefore, only clinically significant VTEs are registered.

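### Section 8.2 leaves the coordinating researcher permanently unblinded for emergency use and does not keep that person away from exclusions, withdrawals or outcome extraction

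*Protocol*

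**What the plan says.** Section 3 describes the design: "This is a double-blind, single center randomized placebo-controlled trial". Section 8.2 says who is blinded and by what means: "Patient, surgical team and anesthesiological team will be blinded for the treatment, as the hospital pharmacy will prepare the infusion bags". The same section then makes one exception: "The coordinating researcher is unblinded in order to be able to consult the treatment arm in case of emergency". No other reason is given for that exception, and no limit is placed on what this person may do.

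Several steps after randomisation involve judgement or data handling:
- Section 4.3 excludes patients during surgery when the bleeding is arterial or comes from surrounding organs or vessels. Section 8.2 has already randomised them after outpatient consent.
- Section 8.4 lets the investigator withdraw a subject and gives the exclusion criteria as an example. Section 8.5 replaces withdrawn subjects.
- Section 8.3 takes staple use, packed cells and postoperative tranexamic acid from the patient record and adds that "rates of postoperative hemorrhage and VTE are obtained from the electronic patient file". It does not say who extracts them.
- Section 12.2 states that source data verification will not be performed.

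On the infusions, Section 6.1 gives the product as "Tranexamic acid injections, 100 mg/ml, ampoule 5 ml". Section 6.6 sets the amount ("A set dose of 1500 mg will be used, based on the study population with morbid obesity") and the preparation: "It will be administered intravenous dissolved in 100 ml sodium chloride 0.9% in a time frame of 15-30 minutes". For placebo, Section 7.6 says: "100 ml sodium chloride 0.9% will be administered in a time frame of 15-30 minutes".

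**The concern.** Emergency unblinding needs a way to learn one patient's arm when the need arises. It does not need a member of the research staff who knows the arms in advance. Section 8.2 gives up the blind for that person without an evident gain in safety, because the pharmacy already holds the information.

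The choice matters more here than it would in many trials. Whether a bleed counts as arterial, and so removes the patient, is closely tied to the primary endpoint of haemostatic clip or staple use. Removed patients are replaced, so a removal changes the analysed set without reducing its size. File-based outcomes will not be checked against source. If someone who knows the arm takes part in any of these steps, the comparison can be shifted, and the monitoring described would probably not detect it.

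The bags are a smaller matter. Section 8.2 rests the blinding of the clinical teams on pharmacy preparation, yet nothing says that the two bags are alike.

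**Working it through.** **1. Is standing knowledge needed for the stated purpose?** Section 8.2 gives emergency consultation as the only reason. The same section has the pharmacy preparing a bag for each patient, from which it follows that the pharmacy knows each arm. The purpose can therefore be met without an unblinded researcher. That the knowledge is standing is inferred from the wording, which describes the person as being unblinded and not as able to break the code.

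**2. Which steps are closed to this person?**

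| Step | Section | Who is named | Closed to the unblinded person? |
|---|---|---|---|
| Information and consent | 11.2 | Clinic doctor | Not stated |
| Exclusion for type of bleeding | 4.3 | Nobody | Not stated |
| Withdrawal | 8.4 | The investigator | Not stated |
| Replacement | 8.5 | Nobody | Not stated |
| Extraction from the file | 8.3 | Nobody | Not stated |
| Check against source | 12.2 | Not performed | Not applicable |

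The text at hand does not say whether the coordinating researcher is also the investigator of Section 8.4.

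**3. How sensitive is the primary test to a single patient?** The planned size comes first. Inputs are the 63.3% clip rate in Section 1 (assumed to be the control rate), the 50% relative decrease in Section 4.4 (giving 31.65%), two-sided alpha of 5% and power of 80%. With unpooled variance:

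n = (1.960 + 0.842)² × [0.633 × 0.367 + 0.3165 × 0.6835] / (0.633 − 0.3165)² = 35.15, so 36 per arm and 72 in total, as in Section 4.4.

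Hypothetical tables, chi-square test without continuity correction:

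| Control with clips | Treated with clips | p |
|---|---|---|
| 23/36 | 15/36 | 0.059 |
| 23/36 | 14/35 (one treated clip patient excluded) | 0.044 |
| 23/36 | 14/36 (that patient replaced by one without clips, or recoded) | 0.034 |
| 32/50 | 23/50 | 0.070 |
| 32/50 | 22/50 | 0.045 |
| 23/36 | 11/36 (about the design effect) | 0.005 |
| 23/36 | 12/36 | 0.009 |

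The rows with 50 per arm correspond to the 100 patients aimed for in Section 3. Close to the threshold, one exclusion or recoding decides the result. At the assumed effect it does not.

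**4. Bag volume.** Drug volume = 1500 mg ÷ 100 mg/ml = 15 ml, which is three 5 ml ampoules.
- If added to 100 ml: 100 + 15 = 115 ml active against 100 ml placebo, a difference of 15/100 = 15%.
- If 15 ml of saline is first withdrawn: 100 ml in both bags, no difference.

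The text of Section 6.6 allows either reading.

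**The case against.** A reader might infer that the blind fails where exclusions and outcomes are judged. The documents do not support that. The surgical team places the clips and sees the bleeding, and Section 8.2 declares both it and the anaesthesia team blinded. Haemoglobin is a laboratory value. Postoperative haemorrhage is defined by transfusion or re-intervention, which are recorded clinical acts. No section gives the coordinating researcher a part in judging any of these. This objection stands in full. What it leaves is that the roles are neither assigned to blinded people nor barred to the unblinded one.

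A reader might also infer that knowledge of past allocations would let someone choose who is enrolled next. Consent is taken by the clinic doctor, randomisation follows it, and the blocks are of variable size, which limits prediction. The documents do not support selective enrolment as a finding.

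Third, the volume difference might be read as a fact that shows staff the arm. The 115 ml figure is only one reading of Section 6.6, and the pharmacy may already match the bags under instructions not shown here. Even if the volumes differ, staff see one bag per patient, and nothing shows that they could name the arm from it.

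Finally, any two-by-two table at the boundary can be tipped by one patient, so the p-values say nothing about how likely a biased decision is. That is correct. They illustrate fragility and do not measure bias.

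**Conclusion.** The point holds in a limited form. Section 8.2 makes a member of the research staff permanently unblinded for a purpose that the pharmacy or a logged code-break could serve, and the protocol does not separate that person from discretionary steps after randomisation or from file-based outcome extraction. That is an avoidable risk to a double-blind trial, and it lies in a rule the protocol itself sets. It is not a demonstrated failure of the blind.

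The size of any bias cannot be derived from the documents. Harm would require the coordinating researcher to take part in exclusion, withdrawal, replacement or extraction, which is an assumption. If so, one patient could decide a borderline primary result (for example, p = 0.059 becoming 0.034), but not a result at the assumed effect (0.005 becoming 0.009).

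The missing statement that the bags match is secondary. The difference is 15 ml (15%) on one reading and zero on the other.

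**What to change.** In Section 8.2, replace the unblinded status of the coordinating researcher with a statement that this person stays blinded until database lock. Place the emergency code-break with the hospital pharmacy or with the logged unblinding of the randomisation system, and record each break.

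In Sections 6.6 and 7.6, state that the pharmacy makes both bags up to the same final volume and identical appearance.

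The cost is a few sentences of protocol text and a pharmacy instruction. No extra staff are needed and the sample size does not change. The small downside is that an emergency unblinding goes through the pharmacy or the system instead of the researcher.
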